### 3.2 Schedule of Assessments

[figure not shown]
**Table 1: Study Assessment and Procedures**

Procedures	Visit 1	Visit 2	Visit 3	Telephone Visit Between Visits 3 and 4	Visit 4	Visit 5 b
	Screening Day -60 to 0	Enrollment Cycle 0	(During 2nd Study Cycle) a	(During Either 3rd or 4th Study Cycle)	(During Either 5th or 6th Study Cycle)	14-30 Days After 7th Study Cycle/ Exit Visit
Written Informed Consent/HIPAA	X					
Eligibility (Inclusion/Exclusion)	X	X				
Medical/Gynecological History c	X	X				
Demographics	X					
Enrollment		X				
Prior History of Contraceptive Use (Past Year)	X	X				
Pre-Trial Medications	X	X				
Vital Signs d	X	X	X		X	X
CBC with Differential and Chemistry c	X					X
HIV Test c	X					
Physical Examination f	X					X
Gynecological Examination g	X	X	X		X	X
Pap Test	X h					
Chlamydia/Gonorrhea Test	X		X i		X i	X i
Urine Culture j	X					X
Dipstick Urinalysis k	X l	X	X		X	X l
Urine Pregnancy Test m	X	X	X		X	X
Serum Pregnancy Test		X				X
Distribute eDiary n		X				
Review eDiary n			X	X	X	X
Dispense/Return Study Product		X o	X		X	X
Subject Satisfaction with Study Product Questionnaire		X	X		X	X
Sexual Satisfaction Questionnaire		X	X		X	X
Pregnancy Intendedness Questionnaire		X	X		X	X
Adverse Events		X	X	X	X	X
Concomitant Medications		X	X	X	X	X
Between-Visit Contact p				X		
Schedule Next Visit/Contact q	X r	X	X	X	X	
Post-Study Treatment Contraception s					X	X

Abbreviations: BV=bacterial vaginosis; CBC=complete blood count; eDiary=electronic diary; HIPAA=Health Insurance Portability and Accountability Act; HIV=human immunodeficiency virus; Pap test=Papanicolaou test; Tel=telephone contact; UTI=urinary tract infection.

- a. The time period between Visit 2 and Visit 3 will vary based subject's first on-study cycle as defined in Figure 1.
- b. Treatment will end after seven study cycles. The cycle at enrollment will be included as one of the seven study cycles only if the time from enrollment to the start of the next menstrual period was  $\geq 21$  days.
- c. Includes documentation of the start date of last menstrual period.
- d. Height, weight, and blood pressure will be measured at Screening. Only weight and blood pressure will be measured at subsequent visits.
- e. Central laboratory will analyze CBC with differential, chemistry panels, and perform HIV test and chlamydia and gonorrhea assessments at Screening. Urine microscopy and culture and Pap tests will be performed locally.
- f. Physical examination to include assessment of heart, lungs, and abdomen, and a breast examination at the discretion of the Investigator.
- g. Gynecological examination is to include a speculum and bimanual examination. Investigators will note the presence or absence of vulvar, vaginal, or cervical findings, including epithelial disruption, or areas of obvious erythema; these will be assessed as either not present, mild, moderate, or severe; the presence or absence of bleeding, petechiae, or sloughing will also be recorded. Clinically significant changes from Baseline as judged by the Investigator are to be reported as AEs. If a woman experiences any significant gynecological symptoms, she should return to the clinical site as soon as possible for a gynecological examination. Wet mount and vaginal pH for monilia, BV, and trichomonas will be performed only for symptomatic women.
- h. Results from a Pap test performed at the screening clinical site  $\leq 12$  months prior to the Screening Visit may be used provided the report is available.
- i. Chlamydia and gonorrhea assessments to be performed at Visits 3, 4, and 5 only if the subject indicates that she has changed sexual partners or is symptomatic. If the subject reports that her partner has been diagnosed or is being treated, she should be assessed/treated as per clinical site standard.
- j. In addition to the urine culture at Screening and Visit 5, subjects will be instructed to contact the clinical site to schedule a dipstick urinalysis and possibly a urine culture any time they suspect they may have a UTI.
- k. If dipstick urinalysis is 1+ for analytes of blood, leukocyte esterase, protein or nitrites, the urine should be sent for urine culture and microscopic urinalysis.
- l. Only to be performed if the subject presents to the clinical site with urinary symptoms. Dipstick urinalysis should be performed at any visit where a subject presents to the center with urinary symptoms.
- m. A urine pregnancy test should be administered any time a subject misses her period or suspects pregnancy. If a subject reports a positive home pregnancy test, a serum  $\beta$ -hCG should be performed.
- n. Subjects will record in their eDiary dates/times of gel use, dates/times of sexual activity, vaginal bleeding, and use of back-up contraception (including reasons for back-up contraception, if applicable). Additionally, subjects will record gel-related genitourinary side effects (vaginal itching, burning, or pain) and assess them as mild, moderate, or severe; these side effects and non-menstrual cycle vaginal spotting/bleeding will be analyzed as AEs. At each visit, Amphora and eDiary compliance data will be reviewed and subjects assessed for re-education. Between visits, sites and subjects will receive alerts if a subject has missed eDiary entries. Sites will record documentation of contact with the subject around eDiary compliance.
- o. Provide instructions on how to use the study drug at Enrollment Visit.
- p. Between-visit telephone contact is to include assessment of AEs, concomitant medications, sexual activity, use of backup contraception, compliance with use of the study drug and eDiary, need for an unscheduled visit, and confirmation of contact information.
- q. Includes confirmation of subject contact information. At the Enrollment Visit and each subsequent study visit/contact, the subject should be reminded to not have intercourse, use the study drug, or place anything in the vagina within 24 hours of the next scheduled visit to the clinical site.
- r. Perform Enrollment Visit upon verification that all eligibility criteria have been met.
- s. At Visit 4, the clinical site staff is to discuss post-treatment contraception with the subject, which would be started at completion of Cycle 7.

**Figure 1: Study Visit Timing Based on Menstrual Cycle at Enrollment**

V=clinical site visit

Visit 5/Exit visit is to take place 14-30 days after the seventh study cycle or from last use of study product for early termination (unless being followed for pregnancy)

Telephone Visit is to take place between V3 and V4

Notes: Duration of Cycle 0 is number of days from enrollment to start of first on-study menstrual period.

## 4 STATISTICAL METHODS

### 4.1 Data Quality Assurance

All tables, figures, and data listings to be included in the report will be independently checked for consistency, integrity and in accordance with standard Health Decisions procedures.

### 4.2 General Presentation Considerations

This section details general policies to be used for the statistical analyses. Deviations from these general policies may be given in the specific detailed sections of this statistical analysis plan. When this situation occurs, the rules set forth in the specific section take precedence over the general policies. The following policies will be applied to all data presentations and analyses:

- All statistical tests will use a 2-sided significance level of  $\alpha = 0.05$ .
- Summary statistics will consist of the number and percentage of responses in each category for discrete variables, and N, mean, median, standard deviation (SD), minimum, and maximum for continuous variables.
- All mean and median values will be formatted to one more decimal place than the measured value. SD will be formatted to two more decimal places than the measured value.
- All percentages will be rounded to one decimal place. The number and percentage of responses will be presented in the form XX (XX.X), where the percentage is in the parentheses. The decimal of the percentage may be dropped due to space constraints when creating a table. The denominator for percentage calculations will be the number of non-missing observations.
- All listings will be sorted for presentation in order of site number, subject number, and date of procedure or event.
- When necessary for analysis purposes, partial dates will be completed (i.e., turned into complete dates) using the most conservative approach.
- All analysis and summary tables will have the population sample size in the column heading.
- Baseline is defined as the last non-missing measurement taken on (prior to treatment) or before enrollment.
- Calculating change from baseline to a visit will be done as follows:  $\text{Change} = \text{Visit} - \text{Baseline}$
- Version 9.4 of SAS or higher will be the statistical software package used to produce all summaries, listings, statistical analyses, and graphs.

### 4.3 Analysis Populations

Intent-To-Treat (ITT): all subjects enrolled into the study.

Safety Population: ITT subjects who use at least one application of the study product.

Modified Intent-To-Treat (MITT): Subjects must meet requirements 1, 2, and 3 simultaneously and at least one of 4 or 5 to be included in MITT:

1. between 18 to 35 years of age (inclusive) at enrollment
2. at least one report of pregnancy after being enrolled (subjects with a positive serum pregnancy test at enrollment will not be included in the MITT population).
3. ITT subjects whose diaries indicate they had at least one episode of coitus while using the assigned study product (also referred as "Typical-Use")
4. have at least 1 cycle without any backup contraception or emergency contraception (EC) recorded in the eDiary product use questionnaire
5. became pregnant and the pregnancy had a conception date that occurred after enrollment and within 7 days of the date of last dose of study product.

Efficacy Evaluable (EE): a subset of the MITT population that includes only those subjects whose diaries indicate that they used the study product correctly for every intercourse for at least one menstrual cycle (also referred as "Perfect-Use" or "Per Protocol"). Cycles in which the study product was used incorrectly for one or more coital acts will be removed, and the correct use cycles will be compressed to provide contiguous cycles of correct use.

The Table 2 provides the handling rules of the analysis populations for special situations.

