9.3 Analysis Populations

The following subject populations will be created:

- Intent-to-treat (ITT): All subjects enrolled into the study.
- Safety population: ITT subjects who administer the study drug at least once
- Modified intent-to-treat (MITT): Subjects must meet requirements 1, 2, and 3 simultaneously, and at least one of requirement 4 or requirement 5 to be included in the MITT analysis population:

- 1. Between 18 to 35 years of age (inclusive) at enrollment
- 2. Had at least one report of pregnancy status after being enrolled; subjects with a positive serum pregnancy test at enrollment will not be included.
- 3. ITT subjects whose diaries indicate they had at least one episode of coitus while using the study drug (also referred as "Typical-Use")
- 4. Had at least one cycle of eDiary without any backup contraception or EC
- 5. Became pregnant and the pregnancy had a conception date that occurred between enrollment and <8 days after final study drug use
- Efficacy-evaluable (EE): A subset of the MITT population that includes only those subjects whose diaries indicate that they used the study drug correctly for every act of intercourse for at least one menstrual cycle (also referred as "Perfect-Use" or "Per Protocol"). Cycles in which the study drug was used incorrectly for one or more coital acts will be removed, and the correct use cycles will be compressed to provide contiguous cycles of correct use.

The MITT is the primary population for analysis of efficacy. Analyses in the EE population will be considered exploratory only.

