- Determining of censoring for cycles to pregnancy: Subjects will be censored from analysis at the earliest of:
 - The estimated date of conception that occurred between enrollment and <8 days after final study drug use
 - The last date at which pregnancy status was known
 - The conclusion of her seventh cycle on-treatment (up to a total of 245 days [or 294 days for the sensitivity analysis, allowing a cycle length range of 21 to 42 days])

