## 1 INTRODUCTION

This Statistical Analysis Plan (SAP) for AMP002, Version FINAL describes the statistical methods to be used during the analyses and reporting of data collected under Phase 3 AMP002 Protocol, dated 01 November 2017. The planned analyses identified in this SAP may be included in the clinical study report (CSR), any regulatory submissions, or future manuscripts. Post-hoc exploratory analyses not identified in this SAP may also be performed to further examine study data and will be clearly identified as such in the final CSR.

This SAP is based upon the following study documents:

- [AMP002-231564\\_Protocol SN0051\\_Version 4.0\\_dated 01-NOV-2017](#)

The structure and content of this SAP provides sufficient detail to meet the requirements identified by the U.S. Food and Drug Administration (FDA) and International Council for Harmonization of Technical Requirements for Pharmaceuticals for Human Use (ICH).

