  - The Pregnancy Review Committee will review all confirmed pregnancies except for subjects who had a borderline or positive b-hCG serum at enrollment, and this information will be provided to data management in an Excel file from the VCAS database. The committee will determine if the pregnancy occurred on-treatment (defined as date of conception between enrollment to <8 days after final study product use) or not on-treatment (defined as date of conception prior to enrollment or after 7 days following final study product use), or whether there is insufficient information for adjudication. The Pregnancy Review Committee assessment of pregnancies being on-treatment or not will be used for the primary endpoint. Pregnancies that could not be adjudicated due to insufficient information will be treated as on-treatment. The medical monitor will review the VCAS file and if the committee provided their own estimated date of conception in the “If disagree, provide rationale” field then the medical monitor will create a new column in the VCAS excel file and will enter into the new column the estimated date of conception provided by the adjudication committee in the “If disagree, provide rationale” field. This re-entry of the estimated date of conception will enable the programming of the statistical analysis.

For confirmed pregnancies, the date of conception will be assessed from the following:

- First trimester transvaginal ultrasound (considered the most accurate; later ultrasounds will not be used for redating)
  - Estimate based on pelvic and/or abdominal examination or pregnancy outcome
  - eDiary information (e.g., last menstrual period and sexual activity)
  - Quantitative  $\beta$ -hCG determination
  - Urine hCG (date of last negative and first positive)
  - Investigator estimation in the absence of above criteria
- Determining of censoring for cycles to pregnancy: Subjects will be censored from analysis at the earliest of:
    - The estimated date of conception that occurred between enrollment and <8 days after final study drug use
    - Date of last study product use + 7 days

- The conclusion of her seventh cycle on-treatment + 7 days (up to a total of 252 days [or 301 days for the sensitivity analysis, allowing a cycle length range of 21 to 42 days])

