#### **4.7.3.5 Summary of Number of Diary Cycles and Cycles Excluded from EE Population**

The average number of diary cycles will be summarized for all MITT subjects through seven cycles. Diaries where backup contraception or EC were used will be excluded unless the subject became pregnant in that cycle. The number of cycles with incorrect use of study product which result in exclusion from the EE analysis will be calculated for each subject and summarized descriptively.

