##### 4.11.1 Determination of Sample Size

Simulation methods are used to evaluate the likelihood of various sample sizes providing enough information to test the primary hypothesis (one-sided Type 1 error of 0.025) and enough use cycles of Amphora gel to address other regulatory requirements. The six month (183 d) cumulative pregnancy percentage was estimated using Kaplan-Meier methods.

The sample size determination assumes the following:

- Study drug pregnancy percentage: 16.5%
- 26.5% of subjects fail to qualify for the primary efficacy analysis population
- Of the subjects that qualify for the primary efficacy analysis population, the average number of evaluable efficacy cycles per subject: 3.17
- Exponential hazard for:
  - Pregnancy rate first 6 months: 16.5%
  - Drop out month 1: 10%
  - Drop out months 2-6: 38%

With 1349 participants aged 18 through 35 years (inclusive), the study will have 90% power to ensure that the upper limit of the 95% CI of the cumulative seven-cycle pregnancy rate is less than or equal to 21%. The expected number of completers is 515 and the expected number of cycles evaluable for safety is at least 3143.

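### SAP 4.3 drops the word *status* from MITT requirement 2, so read literally the primary efficacy population holds only women with a reported pregnancy

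*SAP*

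**What the plan says.** SAP 4.3 (Analysis Populations) defines the MITT by five numbered requirements and combines them as follows: "Subjects must meet requirements 1, 2, and 3 simultaneously and at least one of 4 or 5 to be included in MITT". Requirement 2 reads "at least one report of pregnancy after being enrolled", with a parenthesis excluding women whose serum pregnancy test was positive at enrollment.

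Protocol 9.3 has the same list and the same logic, but its requirement 2 reads "Had at least one report of pregnancy status after being enrolled".

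SAP section 1 says that the SAP covers "data collected under Phase 3 AMP002 Protocol, dated 01 November 2017", which is the protocol version supplied. No SAP sentence announces or explains a change to the MITT.

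Protocol 9.3 makes the MITT the primary efficacy population. SAP 4.7.2 runs the primary Kaplan-Meier test against 21% in it. The typical-use Pearl rate and the efficacy sensitivity tables also use it, and the EE population is a subset of it.

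**The concern.** A report of pregnancy status may be positive or negative. A report of pregnancy, in its ordinary sense, is positive only. Requirement 2 applies to everyone, so meeting requirement 4 (a cycle free of backup and emergency contraception) cannot rescue a woman who has no reported pregnancy. Followed as written, the rule admits women because they had the event that the primary analysis counts.

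A programmer would probably notice, because SAP 4.2 puts the population size in every table heading. The text would then have to be repaired informally, and there is more than one way to do that. One could restore *status*. One could also ignore requirement 2 apart from its enrollment-test exclusion. The second repair admits women with no pregnancy status reported after enrollment, and the SAP's censoring rule would count their time up to last use plus 7 days as event-free. The first scheduled pregnancy test after enrollment is at Visit 3, in the second study cycle, so early dropouts are the women affected. The documents give no count of them, so only the direction can be stated: added event-free time lowers the estimated rate. In an open-label single-arm trial, that choice should be fixed in writing before analysis.

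**Working it through.** **1. Which wording does the rest of the SAP fit?**

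- Requirement 5 (an on-treatment pregnancy) is only an alternative to requirement 4, so women were meant to be able to qualify without a pregnancy.
- SAP 4.7.2.1 censors women at "Date of last study product use + 7 days" or after the seventh cycle, which presupposes members without the event.
- SAP 4.7.3.5 treats pregnancy as an exception among MITT subjects: "Diaries where backup contraception or EC were used will be excluded unless the subject became pregnant in that cycle".
- SAP 4.11.1 assumes that "26.5% of subjects fail to qualify for the primary efficacy analysis population", so 73.5% do qualify, while only 16.5% become pregnant.

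All four fit the protocol wording only. None of them states the rule. The term *pregnancy status* does not occur in the supplied SAP text. The protocol's censoring date that used it, "The last date at which pregnancy status was known" (Protocol 9.8.1.1), is not in the SAP's censoring list either.

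**2. The plan's own figures** (inputs from SAP 4.11.1: N = 1349, 26.5% not qualifying, 3.17 evaluable cycles per qualifying woman, 16.5% pregnancy over 183 days, dropout 10% in month 1 and 38% in months 2-6)

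- Intended MITT: 1349 x (1 - 0.265) = 991.5.
- Cycles: 991.5 x 3.17 = 3143.1 (stated 3143, although labelled there as evaluable for safety).
- Completers: 991.5 x (1 - 0.10 - 0.38) = 515.6 (stated 515).
- Power: Φ((0.21 - 0.165)/SE - 1.96), with the asymptotic Greenwood SE. If the 38% applies to women still in the study, SE = 0.01382 and power = 0.903. If it applies to all women, SE = 0.01406 and power = 0.893 (stated 90%). Simulated power varies with the form of the confidence limit, which the SAP does not specify, but that does not bear on this point.

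The stated figures therefore rest on about 991 women in the primary population.

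**3. Women with an on-treatment pregnancy under the literal text**

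- Lower count: per-cycle risk 1 - 0.835^(1/7) = 2.543%; 3143 x 0.02543 = 79.9, about 80.
- Upper count: simulation of 991 women over 183 days with exponential pregnancy and dropout hazards, 38% applied to women remaining. Mean 124 pregnancies (95% of 2000 runs between 105 and 143); Kaplan-Meier rate in the full population 16.4%.

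**4. Literal Kaplan-Meier rate**

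Women with an off-treatment pregnancy also meet the literal requirement 2. They can enter through requirement 4 and are censored. Their share of reported pregnancies is not in the documents, so a range is assumed. Literal N = on-treatment count / (1 - share).

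| Assumed off-treatment share | N, 183-day model | KM rate, 183-day model | KM rate, 3.17-cycle model |
|---|---|---|---|
| 0% | 124 | 100% | 100% |
| 5% | 131 | 97.1% | 99.2% |
| 10% | 138 | 93.9% | 98.0% |
| 20% | 155 | 86.6% | 94.8% |
| 30% | 177 | 78.5% | 90.0% |

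The 3.17-cycle model uses a constant loss of 26.7% per cycle, at most seven cycles and 79.9 pregnancies; at a 30% share its N is 79.9/0.7 = 114. Over the whole range the literal population is about 80 to 177 women, or 8% to 18% of 991. The off-treatment share would have to reach about 83% (183-day model, grouped into seven cycles) or 90% (3.17-cycle model) before the literal point estimate fell to 21%.

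**The case against.** The strongest reply is that nobody could be misled. The literal reading makes the primary hypothesis meaningless, the SAP names the protocol it serves, and the protocol has the right word. SAP 4.1 requires independent checking of all tables and listings, and planned listing 16.2.3.1 shows the subjects excluded from the MITT, so an almost empty population would be seen. The phrase might also be read loosely as a pregnancy test report, since the parenthesis beside it concerns a serum test. On this view the modelled rates describe an analysis that will not be run.

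Much of this stands. The intent is recoverable, a wrong reported result is unlikely, and the modelled rates are not a prediction. Because the point turns on one missing word, the signed SAP should be checked for it.

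It does not remove the need for the correction. The protocol cannot be assumed to govern wherever the SAP differs, because the SAP departs from it elsewhere: a 252-day rather than a 245-day limit in the censoring rule, Poisson rather than normal-approximation limits for the Pearl rate, and an added requirement of at least one act of intercourse per cycle. Requirements 4 and 5 of this same list were reworded too. A reader cannot tell from the SAP which differences are deliberate. Later checks would detect a problem but would not supply the rule. The changed censoring date is a separate matter, which restoring the word does not settle.

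**Conclusion.** The concern holds. SAP 4.3 as written limits the primary efficacy population to women with a reported pregnancy, contrary to Protocol 9.3. It is a drafting error and not a chosen restriction, but it sits in the definition of the primary population and should be fixed. Under the plan's own assumptions the literal rule replaces about 991 women with about 80 to 177, and a rate assumed to be 16.5% with one of 100% down to about 78%. The counts rest on the SAP 4.11.1 assumptions. The upper count and the lower rate also rest on an assumed off-treatment share of 0% to 30%. The textual conclusion depends on neither.

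**What to change.** Before analysis, restore *status* after *pregnancy* in SAP 4.3 requirement 2 so that it matches Protocol 9.3, and keep the exclusion for a positive serum test at enrollment. As an optional clarification beyond the protocol wording, add that either a negative or a positive result counts as a report. The cost is one word in the SAP. The expected MITT stays at about 991 women and power at about 90%; enrollment, conduct and data collection are unaffected.
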